13.10.4 QOL Questionnaire

The distribution of responses (frequency, percentage) for each of the 9 questions will be summarized at baseline and for each follow-up evaluation at which the survey is administered.

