Swelling, edema	Not present Mild Moderate	45 52 3	Not present Mild Moderate	75 24 1	Not present Mild Moderate	89 9 2	Not present Mild Moderate	89 8 3
Nasal obstruction from tissue edema	Not present Mild Moderate	76 23 1	Not present Mild Moderate	82 13 5	Not present Mild	94 6	Not present Mild Moderate	90 9 1
Disruption of mucosal flow / crusting	Not present Mild Moderate	89 10 1	Not present Mild Moderate	62 34 4	Not present Mild Moderate	84 15 1	Not present Mild Moderate	91 8 1
Blanching	Not present Mild Moderate	29 58 13	Not present Mild	98 2	Not present Mild	98 2	Not present	100
Numbness	Not present Mild Moderate	56 30 14	Not present	100	Not present	100	Not present	100
Soreness, pain	Not present Mild Moderate	70 29 1	Not present Mild	94 6	Not present Mild	99 1	Not present	100
Bleeding at anesthetic injection site (no intervention)	Not present Mild Moderate	51 47 2	Not present	100	Not present	100	Not present	100
Bleeding at treatment site (no intervention)	Not present Mild	85 15	Not present	100	Not present	100	Not present	100
Saddle nose deformity	Not present	100	Not present	100	Not present	100	Not present	100
Bruising around orbital area	Not present	100	Not present	100	Not present	100	Not present	100

Table 2. Treatment Area Observations – TP258 Nasal Valve Pivotal Clinical Study

Table 3. Treatment Area Observations - TP220 Rhinitis Feasibility Clinical Study

Observation	Baseline (% treated nostrils n = 22)	Baseline2-Week Follow-Up $\%$ treated nostrils(% treated nostrils $n = 22$) $n = 20$)		1-Month Follo (% treated no n = 16)	ow-Up strils	3-Month Follow-Up (% treated nostrils n = 8)	
Swelling, edema	Not present9Mild91	Not present Mild	75 25	Not present Mild Not reported	75 12.5 12.5	Not present Mild	75 25
Blanching / color of mucosa	Pale pink 100	Pale pink Hyperemic	90 10	Pale pink	100	Pale pink Not reported	75 25
Obstruction	Not present91Present beyondmid-Meatus9	Not present Present in Ethmoid	90 10	Not present	100	Not present	100
Discharge	Not present45.4Thin36.4Thick18.2	Not present Thin Thick	60 35 5	Not present Thin	87.5 12.5	Not present Thin	87.5 12.5
Scarring / Crusting	Not present 91 Mild 9	Not present Mild Severe	35 50 15	Not present Mild	62.5 37.5	Not present	100

TP668 Ver. 27-NOV-2018

CONFIDENTIAL

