13.0 STATISTICAL CONSIDERATIONS

13.1 Study Design

This study is a prospective, multicenter, nonrandomized, nonsignificant risk (NSR) study of the Aerin Medical InSeca ARC Stylus when used to treat tissue in the posterior nasal nerve area to improve symptoms in those diagnosed with chronic rhinitis. Each subject serves as their own control for comparing baseline condition with postintervention condition.

The design encompasses a 2-phase enrollment. Up to 10 subjects will be enrolled in the first phase. Further enrollment will be suspended until all initial subjects have completed their 4-week evaluation. Information from these patients will be used to assure the safety of the procedure as well as the adequacy of treatment settings and treatment locations. The standard deviation of the change in TNSS score will be used to gauge the appropriateness of the assumption of standard deviation used for study sample size estimation.

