13.5 Missing Data

All efforts will be made to collect all data points in this study. The study hypothesis will be tested using all available data for the subjects in the evaluable patient population. If the primary endpoint is not available for all such subjects, then sensitivity analysis will be performed to assess the potential effect of missing data on the study conclusion. The sensitivity analysis will be performed by imputing all missing data points for the primary endpoint as no (0) improvement. If the study conclusion is upheld using this type of worst-case scenario, no other analysis will be performed. However, if the conclusion using imputed data is different, a multiple imputation approach may be used to gain further insight to the results.

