13.10 Other Efficacy Outcome Measures

13.10.1 Responder Rate

Subjects will be considered to have responded to treatment if they show a decrease of at least 1 point in the rTNSS score at 12 weeks compared to baseline score. An overall responder rate of at least 55% is expected for the study.

13.10.2 rTNSS scores over time

Summary descriptive statistics (mean, SD, median, range) for the rTNSS scores and change from baseline will be summarized at baseline and for each follow-up evaluation.

13.10.3 rTNSS individual nasal symptom scores

The distribution of responses (frequency, percentage) and the mean (SD, median, range) response, based on the 4-point response scale, for each of the survey questions will be summarized at baseline and for each follow-up evaluation.

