13.12 Other Safety Analyses

13.12.1 Nasal Status Assessment

Each component of the assessment will be summarized as frequency and percentage for each level of the categorical variable at baseline and each follow-up evaluation.

TP668 Ver. 27-NOV-2018

CONFIDENTIAL

30 of 43

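### Individual symptoms, QOL and nasal status are summarized only as separate distributions at each visit, so within-subject change and new worsening cannot be read from the planned tables

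*Combined protocol and SAP*

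**What the plan says.** Section 13.1 sets the principle of comparison: "Each subject serves as their own control for comparing baseline condition with postintervention condition". Section 13.9 follows it with a paired test at 12 weeks, Section 13.10.1 with a responder definition based on each subject's own decrease, and Section 13.10.2 with summaries "for the rTNSS scores and change from baseline will be summarized at baseline and for each follow-up evaluation".

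The next outcomes do not follow it:

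- **Individual symptoms (13.10.3).** Frequencies, percentages and means (with SD, median and range) "for each of the survey questions will be summarized at baseline and for each follow-up evaluation".
- **QOL (13.10.4).** "The distribution of responses (frequency, percentage) for each of the 9 questions will be summarized at baseline and for each follow-up evaluation", limited to visits that include the form. No means are planned.
- **Nasal status (13.12.1).** Each component "will be summarized as frequency and percentage for each level of the categorical variable at baseline and each follow-up evaluation".

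None of the three asks for change from baseline, a shift table, a count of worsened subjects, or restriction to subjects with both readings. The synopsis is no more specific. The missing-data rule in Section 13.5 covers only the primary endpoint: "The sensitivity analysis will be performed by imputing all missing data points for the primary endpoint as no (0) improvement".

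**The concern.** In a single-arm study, the contrast between baseline and visit is the only comparison available for these outcomes. Rhinorrhea and congestion also carry their own eligibility thresholds (Section 7.3), so readers will look at them individually.

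Two things go wrong when that contrast is read from two marginal distributions. First, the baseline column contains everyone and the visit column only those who attended, so a difference can arise from who left. Second, improvement in some subjects offsets worsening in others, and the table shows only the net result. The second problem remains when no one is lost. For nasal status, a finding that appears after treatment could be cancelled in the table by resolution of a pre-existing finding in someone else.

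**Working it through.** **Inputs from the plan.** N = 50 and 10% dropout and nonevaluable (Section 13.3). Visits run to 52 weeks (Table 1). The 10% belongs to the sample size for the 12-week endpoint; no loss rate is given for 26 or 52 weeks.

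**The plan's own figure.** An exact paired t-test with one-sided alpha 0.05, a mean 1 point beyond the null and SD 2 gives n = 36 with power 90.3%, as stated; 36/0.90 = 40. The sample size is not in dispute here.

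**Step 1: attrition with no true change.** Let *a* of N subjects have a finding at baseline, let *k* leave, *j* of them affected, and let nobody change. The share at follow-up is (a − j)/(N − k). With N = 50 and k = 5, the extremes are j = 5 and j = 0. The baseline shares are assumptions, since the documents give none for this trial.

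| Assumed baseline share | All 5 losses affected | All 5 losses unaffected |
|---|---|---|
| 20/50 = 40% | 15/45 = 33.3% | 20/45 = 44.4% |
| 15/50 = 30% | 10/45 = 22.2% | 15/45 = 33.3% |
| 10/50 = 20% | 5/45 = 11.1% | 10/45 = 22.2% |

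The false improvement is at most 6.7 to 8.9 points, and the false worsening at most 2.2 to 4.4 points. A table restricted to subjects with both readings would show zero change in every cell.

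These are worst cases. If loss were unrelated to status, the chance that all 5 losses came from the 20 affected subjects would be C(20,5)/C(50,5) = 15,504/2,118,760 = 0.7%.

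**Step 2: the same effect on a symptom mean.** Assume 20 subjects score 3 and 30 score 2: the mean is (60 + 60)/50 = 2.40. Remove five who score 3: (45 + 60)/45 = 2.33, with no change in anyone.

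**Step 3: hidden worsening with full follow-up.** With *a* affected at baseline and *f* at the visit, the number newly affected can be anything from max(0, f − a) to min(f, N − a).

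- a = 15, f = 15, N = 50: from 0 to 15.
- a = 20, f = 10, N = 50: from 0 to 10. An apparent fall from 40% to 20% could be 10 resolved and none new, or 20 resolved and 10 new.

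**Step 4: what Table 3 can and cannot show.** Table 3 (TP220) reports 22 nostrils at baseline and 8 at 3 months. Free of swelling: 9% of 22 = 2, then 75% of 8 = 6. Mild swelling: 20 of 22, then 2 of 8. If none or all of the 14 unseen nostrils were swollen, mild swelling at 3 months would lie between 2/22 = 9% and (2 + 14)/22 = 73%. Both bounds are below the 91% baseline. Taking the 8 as a subset of the 22, at most 2 of the 6 swelling-free nostrils were free at baseline, so at least 4 changed.

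**The case against.** **These are descriptive summaries.** They carry no hypothesis, threshold or success criterion, and the primary test is paired. This stands and limits the weight of the point.

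**Other parts of the plan already help.** Section 13.7 reports follow-up by visit, but that shows how many are missing, not how their baseline values differed. Section 13.10.3 gives means; with complete data their difference is the mean change, but the spread of change and the number worsened still cannot be recovered, and QOL and nasal status have no means. The four symptoms also feed the total rTNSS, which is analysed as change, but a total does not show which symptom moved.

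**A reader might infer that Table 3 is an example of attrition passing for improvement.** It is not. By Step 4 the fall in swelling survives the worst case; only its size is uncertain. The table also prints n per visit, and Table 2 uses the same format while falling only from 99 to 96 nostrils by 26 weeks.

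**A reader might also infer that these are the only planned summaries of local tissue safety.** They are not. Under Sections 8.5 and 12.1, observations that need mitigation or go beyond what is anticipated become adverse events, and Section 13.11 lists those individually. What remains is the range below that threshold. It is not empty: the tables of anticipated observations include moderate grades (Table 2) and 15% severe scarring or crusting at 2 weeks (Table 3).

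**An improved/unchanged/worsened count needs an ordered scale.** The documents do not show the QOL response options, and some Table 3 components, such as mucosal color or the location of obstruction, are not clearly graded. A blanket rule of taking the worse nostril therefore has no basis in the documents for every component. This stands, and the fix is limited accordingly.

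**Conclusion.** The point holds as a low-cost improvement to three descriptive analyses. As written, Sections 13.10.3, 13.10.4 and 13.12.1 cannot separate within-subject change from a change in who is observed, and cannot show how many subjects newly worsened.

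The attrition effect is modest at the plan's 10%: no more than about 9 points in the cases worked here, only if losses are concentrated in one group, and in either direction. It could be larger if loss by 52 weeks exceeds 10%, for which the documents give no figure. The hidden-worsening problem does not depend on loss at all: 15/50 at both times fits 0 to 15 new cases. For nasal status it matters for observations below the adverse-event threshold.

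The illustrations rest on assumed baseline shares. The conclusion about the primary endpoint is unaffected.

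**What to change.** - **13.10.3:** add the mean within-subject change with a 95% confidence interval for each of the four symptoms at each follow-up visit.
- **13.10.4 and 13.12.1:** add baseline-by-visit shift tables among subjects with both readings, showing the paired n and the number missing. Give improved, unchanged and worsened counts where the response scale is ordered.
- **13.12.1:** also list findings that were absent at baseline or, for graded components, are of higher grade than at baseline.

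The existing per-visit summaries can stay. The readings are already scheduled in Table 1, so there are no new visits, subjects or sample size. The cost is SAP wording and a few extra tables.

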13.10.5 Subject Satisfaction Survey

The distribution of responses (frequency, percentage) and the mean (SD, median, range) response, based on the 10-point response scale, for each of the survey questions will be summarized for each follow-up evaluation at which the survey is administered.

13.11 Primary Safety Endpoint Analysis

Safety will be assessed by characterizing the type and frequency of adverse events reported at or following the study procedure, and throughout the follow-up period. Event types include:

- Serious Adverse Events, including Deaths
- Serious Adverse Device Effects
- Unanticipated Adverse Device Effects
- Device Related Serious Adverse Events

The number of events as well as the percentage of subjects experiencing each event type will be calculated.

All adverse events will be analyzed for all enrolled subjects. Adverse events will be coded using a standardized dictionary, so that adverse events may be categorized for analysis at an appropriate level of detail. Listings will be provided to detail individual events. The number of subjects, number of adverse events, and the proportion of subjects reporting each adverse event will be summarized. Seriousness and severity of adverse events and their relationship to the device and/or procedure will be summarized. A time course of adverse events will be presented using the intervals:

- 0 days to 2 weeks
- 2 weeks to 4 weeks
- 4 weeks to 12 weeks
- 12 weeks to 26 weeks
- 26 weeks to 52 weeks

Narratives will be presented for all deaths, serious adverse events, serious adverse device effects, unanticipated adverse device effects, and subjects withdrawn due to an adverse event.

13.12 Other Safety Analyses

13.12.1 Nasal Status Assessment

Each component of the assessment will be summarized as frequency and percentage for each level of the categorical variable at baseline and each follow-up evaluation.

TP668 Ver. 27-NOV-2018

CONFIDENTIAL

30 of 43

13.12.2 VAS Pain Scores

VAS pain scores will be summarized descriptively (mean, median, standard deviation, minimum, and maximum) at the immediate post-treatment evaluation and at the 2-, 4-, and 12-week follow-up evaluations.

13.12.3 Medications

Medications and indications will be summarized and reviewed for significant trends. Full detailed listings will be provided by subject.

14.0 SAFETY RELATED STOPPING RULES

The study sponsor will be charged with monitoring the study for safety and for auditing the quality of the data. If there are any perceived safety concerns related to the InSeca ARC System or procedure, the trial may be terminated.

15.0 QUALITY ASSURANCE AND SUPERVISION BY AUTHORITIES

This study will be conducted in accordance with elements of the Good Clinical Practice E6(R2): Integrated Addendum to ICH E6(R1) (March 2018), abbreviated requirements of 21 CFR 812.2(b) for Non-significant Risk (NSR) device studies, the Declaration of Helsinki, the Belmont Report, and IRB/EC requirements.

All documents and data shall be produced and maintained in such a way to assure control of documents and data to protect the patient's privacy as far as reasonably practicable. The Sponsor and representatives of the FDA or other regulatory authorities are permitted to inspect the study documents (e.g., study protocol, CRFs, and original study-relevant medical records/files) as needed. All attempts will be made to preserve patient confidentiality.

All clinical sites are subject to audit by study sponsor personnel or designee for protocol adherence, accuracy of CRFs and compliance with applicable regulations. Any evident pattern of non-compliance with respect to these standards will be cause for corrective action.

The study protocol, data-recording procedures, data handling as well as study reports are subject to an independent clinical Quality Assurance audit by the study sponsor, its designee, or health authorities.

16.0 STUDY MANAGEMENT

This study will be conducted in accordance with elements of the Good Clinical Practice E6(R2): Integrated Addendum to ICH E6(R1) (March 2018), Abbreviated Requirements of 21 CFR 812 for NSR device studies, the Declaration of Helsinki, the Belmont Report and any conditions imposed by the reviewing IRB or US FDA or other regulatory agency.

The study sponsor has the overall responsibility for the conduct of the study according to all applicable regulatory requirements. The study sponsor will have certain direct responsibilities and will delegate other responsibilities to the Principal Investigator. The study sponsor and Principal Investigator will ensure that the study is conducted according to all applicable regulations. All personnel to participate in the conduct of this clinical trial will be qualified by education and / or experience to perform their tasks.

The study sponsor, Investigator or any person acting for or on behalf of a sponsor or Investigator shall act in accordance the applicable standards, guidelines and regulations.

17.0 DEVICE MANAGEMENT

Devices used in this study will be labeled with the study protocol number and controlled in a manner consistent with investigational devices. The investigator shall maintain adequate records of the receipt and disposition of all study devices. When study enrollment is complete, the investigator shall return any unused devices to the sponsor or their designee. The device will only be used as part of this study in eligible patients and will be used according to its intended use. A copy of the Instructions for Use (IFU) accompanies each study device.

18.0 REQUIRED DOCUMENTS FROM THE INVESTIGATOR (PRIOR TO STUDY START)

At a minimum, the following documents will be provided by the study site to the study sponsor:

- Clinical Trial Agreement signed by the Investigator or responsible party at the Investigator's facility
- Signed Investigator Agreement
- Signed Clinical Protocol Signature Page
- IRB Site Approval Letter
- IRB Site Approved Informed Consent Form (ICF)
- Current Curriculum Vitae (initialed and dated) from all investigators and study coordinators
- Current Medical Licenses from all investigators and licensed study coordinators
- Evidence of GCP training (for all investigators and study coordinators)
- Financial disclosure from all investigators
- Delegation of Authority log

A site may not begin study participation until all the above listed documents have been provided to the study sponsor.

19.0 TRAINING

The InSeca ARC System is intended for use by experienced medical personnel. Any site personnel who will perform the procedure (i.e., the Investigator and appropriate sub-investigators) will be provided training by the study sponsor to familiarize them with the use of the InSeca ARC System prior to their participation in the clinical study.

Each study center will undergo study initiation including but not limited to a review of the following:

- Study Protocol
- Procedures for obtaining Informed Consent
- Procedures for completing Informed Consent Form
- Reporting requirements, including those associated with the handling of adverse events
- CRF completion and correction procedures

CONFIDENTIAL

- InSeca ARC System overview / Device usage instructions
- Good Clinical Practices (GCP) overview
- Protection of patient confidentiality

20.0 ETHICAL CONSIDERATIONS

The rights, safety and wellbeing of clinical study subjects shall be protected consistent with the ethical principles outlined in the Declaration of Helsinki. This shall be understood, observed and applied at every step in this clinical study.

It is expected that all parties will share in the responsibility for ethical conduct in accordance with their respective roles in the study. The Sponsor and the Investigator shall avoid improper influence or inducement of the patient, study monitor, clinical investigator or other parties participating in or contributing to the study.

21.0 PROTECTION OF PATIENT CONFIDENTIALITY

At all times throughout the clinical study, confidentiality will be observed by all parties involved. All data shall be secured against unauthorized access. Privacy and confidentiality of information about each patient shall be preserved in the reports and in any publication. Each patient participating in this study will be assigned a unique identifier. All CRFs will be tracked, evaluated, and stored using only this unique identifier.

The study site will maintain a confidential study patient list (paper or electronic) identifying all enrolled patients. This list will contain the assigned study patient's unique identifier and name. The Site Principal Investigator (PI) bears responsibility for keeping this list confidential. This list will not be provided to the study sponsor and is only to be used at the study center.

Monitors and auditors will have access to the study patient list and other personally identifying information of study patients to ensure that data reported in the CRF corresponds to the person who signed the ICF and the information contained in the original source documents. Such personal identifying information may include, but is not limited to the patient's name, address, date of birth, gender, race and medical record number.

NOTE: The patient's name, medical record number or address will NOT be recorded in the monitor's visit report or the database; demographic data that may be recorded includes age, race, and gender.

Any source documents copied for monitoring purposes by the Sponsor will have patient identifiable information redacted and be identified by using the assigned patient's unique identifier to protect patient confidentiality.

22.0 DATA COLLECTION

Study data will be collected using standardized Case Report Forms (CRFs). The CRFs are designed to accommodate the specific features of the trial design. Modification of CRFs will only be made if deemed necessary by the study sponsor.

23.0 SOURCE DATA VERIFICATION

At a minimum, source data verification will be performed on all primary endpoint, outcome measures, and safety data for each patient enrolled in this study.

24.0 STUDY SUSPENSION OR EARLY TERMINATION

The study can be discontinued at the discretion of the Site PI or Sponsor for reasons including, but not limited to, the following:

- Occurrence of adverse events unknown to date in respect to their nature, severity, or duration, or the unexpected incidence of known adverse events
- Obtaining new scientific knowledge that shows that the study is no longer valid or necessary
- Insufficient recruitment of patients
- Unanticipated adverse device effect (UADE) presenting an unreasonable risk to patients (Sponsor may terminate the study immediately)
- Persistent non-compliance with the protocol
- Persistent non-compliance with IRB/EC or regulatory requirements

If the study is discontinued or suspended prematurely, the Sponsor shall promptly inform all clinical investigator(s) / study center(s) of the termination or suspension and the reason(s) for this. The IRB/EC shall also be informed promptly and provided with the reason(s) for the termination or suspension by the Sponsor or by the Site PI / study center(s). Regulatory authorities and the personal physicians of the patients may also need to be informed if deemed necessary.

